4.1 Selection of the Study Population

All clients attending a participating outlet on the day selected for exit interviews will be eligible to be screened for inclusion into the interview sample. Only those who meet all the criteria will be counted towards the sample size.

4.2 Inclusion/Exclusion Criteria

OUTLETS: Only outlets who are registered with the Kenya Pharmacy and Poisons Board and who stock ACTs will be asked to participate

PARTICIPANTS-

INCLUSION CRITERIA:

- Participants with fever, or history of fever in the last 48 hours, or suspects they may have malaria
- Individual with malaria-like illness must be present at recruitment
- Older than one year of age

EXCLUSION CRITERIA:

- Any individual with signs of severe illness requiring immediate referral
- Individuals who have taken an antimalarial in the last seven days, including for the current illness
- Patients <18 years without a parent or legal guardian present
- Adults who are unable to consent for themselves

5 STUDY PROCEDURES/EVALUATIONS

5.1 Study Procedures

On random days of the month, clients leaving the pharmacy will be asked to participate in a brief survey. Those who meet the inclusion/exclusion criteria will provide verbal consent before responding to questions about their current illness and their decisions regarding testing and medicines purchased. These clients will have been offered an RDT at the pharmacy if they have malaria-like symptoms. RDTs will be available in all participating pharmacies at the same price. Those who do not wish to purchase an RDT are free to conduct their transaction as planned.

The exit survey will be conducted in one session and last approximately 15-20 minutes.

5.2 Laboratory Evaluations

None

6 STATISTICAL CONSIDERATIONS

6.1 Study Outcome Measures

The primary outcome measure is the proportion of all ACTs that are sold to individuals with a positive malaria diagnostic test defined as anyone who is tested at the outlet and receives a positive test result or is referred from a health facility with a documented positive test result.

Among secondary outcomes, behavior will be measured for individuals who were tested at the outlet. Untested clients are those who chose not to be tested and did not come with a test result from another facility. The major secondary outcome is the proportion of suspected malaria cases that are tested. This outcome will allow us to determine whether the conditional subsidy can drive demand for testing. Note that “untested people” here refers specifically to individuals that present at the shop without a referral but decline to be tested

people who were tested with an RDT

people who were tested with an RDT + # untested people who purchased an antimalarial

Other secondary outcomes will measure 1) adherence to the RDT result among all those tested at the outlet, 2) proportion of all suspected malaria cases that are managed appropriately (tested for malaria, and use ACT following a positive test or do not purchase an ACT after a negative test), and 3) ACT use by untested clients.

- Secondary outcome 2: Adherence to the RDT result among all those tested in the shop

people who tested positive and purchased ACT + # people tested negative and did not purchase any AM
people who were tested with an RDT

For those who are negative, if they buy any antimalarial (AM), including monotherapies and older therapies, they are not adhering to test result.

- Secondary outcome 3: Proportion of all suspected malaria cases that are managed appropriately in the shop

people who tested positive and purchased ACT + # people tested negative and did not purchase any AM
people who were tested with an RDT + # untested people who purchased an antimalarial

“Untested people” here refers specifically to individuals that present at the shop without a referral but decline to be tested

- Secondary outcome 4: ACT use among untested clients

people who were not tested in the shop and purchased an ACT
people who were not tested in the shop, did not have documentation of test and purchased any AM

For the primary outcome, we include in both numerator and denominator those individuals who were referred from a health facility with a documented positive test result. That is, for the

primary outcome we are interested in evaluating the degree to which the interventions impacted the purchasing behavior of all suspected malaria cases seeking treatment. Our secondary outcomes do *not* include these individuals (i.e. the outcomes are calculated on the subset of individuals that present at the shop for testing without a referral). That is, for the secondary outcomes we are specifically interested in evaluating the degree to which the interventions impacted purchasing behavior among individuals who present at the shop for testing.

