In order to align both the provider and customer incentives towards testing and targeting, the provider must be willing to perform the test and sell the appropriate medicine and, at the same time, the customer must be motivated to purchase the test and adhere to the results. We hypothesize that offering ACT subsidies for the client (conditional on a positive test), and incentives to the provider to offer malaria testing, will each, on their own, have a very modest impact on uptake of testing and targeting of ACTs in the retail sector. We further hypothesize that when combined, they will have a synergistic effect on RDT testing and ACT targeting. However, it is important to estimate the effect of each intervention separately and in combination in order to provide cogent evidence to support joint implementation. We will test the combination of subsidies for ACTs and RDTs (selected from Aim 1) paired with a provider-directed testing incentive in a four-arm cluster-

randomized controlled trial to evaluate their impact on the proportion of ACTs sold to individuals with parasitologically-confirmed malaria among those seeking care in the retail sector.

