2.16	Did the client show documentation of the prescription?	
1. No
 
2. Yes, a written prescription from the provider/facility/lab
 
3. Yes, other (Specify: _____)
	

Section 3: Test at Shop

Number	QUESTION	RESPONSE	SKIP
3.1	Did you (or your child) have your blood tested for malaria today at the shop?	
1. Yes
 
2. No
	If yes skip to 3.3
3.2	Why not? (Mark all that apply)	
1. Too expensive
 
2. RDT was not offered
 
3. RDT not in stock
 
4. No time
 
5. Already sure illness is malaria
 
6. Already sure illness is not malaria
 
7. Don't want to get finger pricked
 
8. Was tested elsewhere before coming
 
9. Had a prescription for drug I needed before coming
 
99. Other Specify: _____
	Next skip to section 4
3.3	RDT results from shop (self-report)	
1. Negative
 
2. Positive
 
3. Invalid
	
3.4	How likely is it that the result of the test was correct? Only if tested	
1. Not possible
 
2. Unlikely but not impossible
 
3. 50/50
 
4. Likely
	

		5. Absolutely sure Don't know	
--	--	----------------------------------	--

Section 4: Purchase Questions

Number	QUESTION	RESPONSE	SKIP
4.1	Which medicine(s) did you obtain from the shop today to treat your/your child's illness Choose all that apply,	
 1. AL (Lonart/CoArtem/Artefan) 2. Other ACT (DHAP, DP, Duocotexin, P-alaxin) 3. Other antimalarial (Artesunate injection, Quinine, Chloroquine, SP/Fansidar) 4. Antibiotic (Amoxyl/Ceptrin, Metronidazole/Flagyl/Ampicillin) 5. Painkiller/fever medicine (Panadol/Brufen/Hedex/ Action/Maramoja) 6. Cough medicine or decongestant 7. Other _____ 8. None 
99. Don't know
	If 2, 3, 4, 5, 6, 7 or 99 Skip to 4.4 If 8, skip to 5.1
4.2	How much did you pay today for the ACT? (The amount refers to how much money respondent paid for the ACT. Don't add the amount of the voucher if any was used-the amount should be between 0-5000, or 9999 for don't know)	ACT= _____ KES OR Don't know/remember...9999	
4.3	How much did you spend at the pharmacy today? (Total cost to client including RDT, ACT and any other drugs)	_____ KES	
4.4	Was there any discount for your ACT at the shop today?	
 1. Yes 2. No 3. Don't know 	

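### The written definition of untested clients drops those never offered an RDT from testing uptake and secondary outcome 3, so any effect of the provider incentive through more offering is missed there

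*Combined protocol and SAP*

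**What the plan says.** Section 6.1 names the outcome broadly: "The major secondary outcome is the proportion of suspected malaria cases that are tested". Its denominator is "people who were tested with an RDT + # untested people who purchased an antimalarial", and secondary outcome 3 uses the same denominator.

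The section then narrows who counts as untested. A general sentence for the secondary outcomes reads "Untested clients are those who chose not to be tested and did not come with a test result from another facility". The note to testing uptake reads "Note that “untested people” here refers specifically to individuals that present at the shop without a referral but decline to be tested", and the same restriction, "individuals that present at the shop without a referral but decline to be tested", is repeated under secondary outcome 3. The formula for secondary outcome 4 differs: it counts clients not tested in the shop and does not ask why.

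Three other places bear on this:

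- Section 5.1 says of interviewed clients: "These clients will have been offered an RDT at the pharmacy if they have malaria-like symptoms".
- Appendix A.1, item 3.2, lists "RDT was not offered" as a reason for no test, with a separate option for an RDT stock-out.
- Section 1.1 says that, for incentives to align, "the provider must be willing to perform the test and sell the appropriate medicine", and describes the provider incentive as one for offering tests. Section 3 pays outlets in Arms 2 and 4 for RDTs.

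Section 6.2 plans Arm 4 against each of Arms 1, 2 and 3. Section 6.4 applies the primary model to the secondary outcomes.

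**The concern.** A client who was never offered a test, or who met a stock-out, has neither declined nor chosen. Under the written definition that client is not untested, and was not tested either, so the client enters neither part of the denominator. Testing uptake then measures acceptance among clients who were offered a test, which is a different quantity from the one the outcome names.

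This matters because Arms 4 and 3 differ only by the provider incentive, and making providers offer more tests is one way that incentive is meant to work. Arm 4 v Arm 1 contains the same component. Both arms of Arm 4 v Arm 2 carry the provider incentive, so the point bears less on that comparison. Testing uptake is the major secondary outcome and has its own power statement in section 6.2.

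**Working it through.** No figure in the plan depends on this definition. The one number attached to testing uptake is the section 6.2 power statement (over 89% for 16 points). It comes with no baseline testing rate, offer rate or ICC for testing, so there is nothing to reproduce. The check is algebraic.

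**Inputs, all assumed because the documents give none of them**

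- *o*: share of unreferred clients offered an RDT that is in stock
- *a*: share of those offered who accept
- *b*: share of clients without a test who buy an antimalarial, taken as equal for decliners and the never-offered

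**Step 1. Split of clients.** Tested: *oa*. Declined: *o*(1 − *a*). Not offered or no stock: 1 − *o*.

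**Step 2. Uptake as written (decliners only).** *oa* / [*oa* + *o*(1 − *a*)*b*] = *a* / [*a* + (1 − *a*)*b*]. The offer rate cancels.

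**Step 3. Uptake with all untested antimalarial buyers.** *oa* / [*oa* + (1 − *oa*)*b*]. The offer rate remains.

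**Step 4. Offering only.** Let *o* be 40% without and 80% with the provider incentive, with *a* the same in both.

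| *b* | *a* | All untested, *o* = 40% | All untested, *o* = 80% | Difference | As written, both arms |
|---|---|---|---|---|---|
| 1 | 30% | 12.0% | 24.0% | +12.0 | 30.0% |
| 1 | 40% | 16.0% | 32.0% | +16.0 | 40.0% |
| 1 | 60% | 24.0% | 48.0% | +24.0 | 60.0% |
| 0.8 | 30% | 14.6% | 28.3% | +13.7 | 34.9% |
| 0.8 | 40% | 19.2% | 37.0% | +17.8 | 45.5% |
| 0.8 | 60% | 28.3% | 53.6% | +25.3 | 65.2% |

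Example, *b* = 0.8 and *a* = 40%: 0.16/(0.16 + 0.84 × 0.8) = 19.2%; 0.32/(0.32 + 0.68 × 0.8) = 37.0%; as written 0.4/(0.4 + 0.6 × 0.8) = 45.5% in both arms. The written difference is 0 in every row.

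**Step 5. Acceptance also moves (*b* = 1, same offer rates).**

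- Acceptance falls from 60% to 50% as offering widens: all untested 0.4 × 0.6 = 24% v 0.8 × 0.5 = 40% (+16); as written 60% v 50% (−10). The sign reverses.
- Acceptance rises from 40% to 50%: all untested 0.4 × 0.4 = 16% v 0.8 × 0.5 = 40% (+24); as written 40% v 50% (+10). Part of the effect is kept.

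**Step 6. Secondary outcome 3.** Its numerator is the tested clients who followed the result. With *h* the share of tested clients who did so (secondary outcome 2), it equals *h* × uptake on the same denominator. The offer rate therefore cancels here too, unless *h* itself changes with offering.

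**Step 7. Universal offering.** With *o* = 1, steps 2 and 3 give the same expression and the definitions agree.

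**The case against.** **The wording may only be loose.** The note's main work is to set aside referred clients, as the end of section 6.1 explains. The outcome's name, the secondary outcome 4 formula and the agreement indicators in section 3 carry no condition of declining. An analyst who coded item 3.1 = No would keep the clients in question. That is a fair reading of intent, but it departs from a restriction that is explicit and repeated. Section 6.1 as it stands supports two codings that can give different results.

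**Everyone is offered a test.** Section 5.1 says so, and section 6.3 provides an initial free RDT stock and visits at least monthly that check stock and testing. If that holds, nothing is lost. This part stands, and makes the harm conditional. Item 3.2, however, provides for both failures, and section 1.1 notes that a test can cost the retailer a sale.

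**The outcome is about client demand.** Section 6.1 says it should show whether the conditional subsidy drives demand for testing, and acceptance among those offered is relevant to that. This supports reporting acceptance alongside. It does not support replacing the named proportion, which is also compared between arms that differ only in the provider incentive.

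**A payment per test may also raise acceptance.** That stands. The written ratio would pick up that part (step 5), so a null result is not the general expectation.

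**Conclusion.** The point holds as a defect in a written outcome definition. Applied literally, section 6.1 removes never-offered and stock-out antimalarial buyers from testing uptake and secondary outcome 3. Whatever part of the provider incentive's effect works through more offering is then missed in Arm 4 v Arm 3 and Arm 4 v Arm 1 on those two outcomes. The cancellation in step 2 is algebra, given equal *b* in decliners and the never-offered. The sizes in steps 4 and 5 are illustrations on assumed rates. The true size is unknown, and is zero if every client is offered a test.

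A reader might infer more, and the documents do not support it:

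- *The incentive's effect is hidden from the trial.* The primary outcome covers all ACTs sold, including to clients never offered a test, and the secondary outcome 4 formula counts anyone not tested in the shop. Neither is affected.
- *The two outcomes will show no effect.* That requires the incentive to act through offering alone, which the documents do not say.
- *Uptake is most overstated in the control arm.* That assumes offering is lowest there; no offer rates by arm are given.
- *Arm 2 v Arm 1 is damaged.* It is not among the planned comparisons.

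**What to change.** 1. In section 6.1, define untested once: item 3.1 = No, for any reason in item 3.2, among clients without a referral and without a test result from another facility (items 2.8 to 2.10). Use it in testing uptake and in secondary outcomes 3 and 4. The outside-result condition must stay; otherwise clients who were tested elsewhere, which is itself an item 3.2 option, would count as untested. State that clients routed past item 2.8 by item 2.5 count as having no outside result.
2. Report the item 3.2 reasons by arm (not offered, out of stock, other), with a rule for clients who mark several. Add acceptance among those offered as a supplementary measure of client demand.
3. Reconcile the section 5.1 statement that clients will have been offered an RDT with the item 3.2 options, so that the analysis does not assume universal offering.

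The cost is wording and one added table, since the items are already in the exit interview. Reported uptake may be lower. The change should be settled before unblinded results are seen.

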The objective of this study is to test the effect of provider-directed and patient-directed incentives on improving the management of suspected malaria fevers that receive care in the retail sector. Provider-directed incentives include small payments for taking the time to conduct malaria-RDT testing for participants with malaria-like illness. Patient-directed incentives are inexpensive RDT testing coupled with a conditional ACT discount. The ACT discount is only applied if the RDT is positive for malaria. Outcomes will be measured by exit interviews on random days each month at each participating outlet.

Primary:

- The primary outcome will be the proportion of all ACTs that are sold to individuals with a positive malaria diagnostic test. For this outcome, a positive test is anyone who has a malaria-RDT performed at the outlet and receives a positive result or is referred from a health facility with a documented positive test result.

Secondary:

- The major secondary outcome is the proportion of suspected malaria cases that are tested. This outcome will allow us to determine whether the conditional subsidy can drive demand for testing.
- Other secondary outcomes will measure 1) adherence to the RDT result among all those tested at the outlet, 2) proportion of all suspected malaria cases that are managed appropriately (tested for malaria, and use ACT following a positive test or do not purchase an ACT after a negative test), and 3) ACT use by untested clients.

For questions regarding this protocol, contact:

Individuals: DMID Representative:

[name], MPH
Clinical Project Manager NIH/NIAID/DMID/PIPB
[name]
[contact]
[contact]

Principal Investigator: *Site investigator responsible for conducting the study:*

[name] [name]
Associate Professor of Medicine and Global Health, Duke University
[name]
[contact]
[contact]

Subcontract Principal Investigators:

[name]

Senior Manager, Malaria Commodity Access, Clinton Health Access Initiative
[name]
[contact]
[contact]
[contact]

[name]

Lecturer, Department of Medicine, Moi University School of Medicine
[name]
[contact]
[contact]
[contact]

Institutions:

Duke University

[name]
[name], Lead Grants and Contracts Administrator, DGHI
[contact]
[contact]
[contact]

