2 OBJECTIVES

The ultimate goal of a conditional subsidy scheme is to limit both inappropriate use of ACTs by those without a test or with a negative test, as well as to reduce the programmatic cost of ACT subsidies by offering them conditionally on a positive test at the point of sale. The objective of this study is to test the effect of provider-directed and patient-directed incentives on improving the management of suspected malaria fevers that seek care in the retail sector.

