Data for our main study outcomes will be collected by exit interviews with customers in order to avoid bias that may arise by relying on provider-reported data. In previous retail-sector studies, results from exit interviews and provider reports differed significantly, with exit interview results considered more reliable [22, 26]. Trained data collectors will approach customers who have transacted at the outlet and ask them if they are willing to participate in an exit interview. In our experience, refusal rates are less than 2% for these types of surveys so we expect our sample to accurately represent all transactions at the outlet. Customers will be eligible if they sought treatment for a febrile illness or malaria-like symptoms for themselves or their child, provided the child is present. Exit interviews will be conducted on randomly selected days each month and data collectors will be randomly assigned to outlets in order to minimize behavior change prompted by the presence of the interviewer. The number of days of data collection at each outlet will depend on the sales volume with a target of 10 participants per outlet per month. Customers will be asked to report whether they had a test, the results of the test, and what medicine they purchased. Basic information about household assets will also be collected in order to stratify participants on socioeconomic status.

Exit interview and provider reporting data will be compared to assess agreement between the sources. Specifically, we will compare the following indicators aggregated by outlet: the proportion tested, the proportion of tests positive and, the proportion of individuals using ACTs by test status (untested, positive or negative).

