The primary outcome will be the proportion of all ACTs that are sold to individuals with a positive malaria diagnostic test. The ultimate goal of a conditional subsidy scheme is to limit both inappropriate use of ACTs by those without a test or with a negative test as well as to reduce the programmatic cost of ACT subsidies by offering them conditionally on a positive test at the point of sale. For this outcome, a positive test is anyone who is tested at the outlet and receives a positive result or is referred from a health facility with a documented positive test result. Although all ACTs purchased after a test, whether tested at the outlet or health facility, are included in the outcome measure, only ACTs purchased following a *test at the outlet* are eligible for the conditional subsidy. Our major secondary outcome is proportion of suspected malaria cases that are tested. This outcome will allow us to determine whether the conditional subsidy can drive demand for testing. Other secondary outcomes will measure 1) adherence to the RDT result among all those tested, 2) proportion of all suspected malaria cases that are managed appropriately (tested for malaria, and use ACT following a positive test and do not purchase an ACT after a negative test), and 3) ACT use by test status (untested, negative, positive).

4 Study Population

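### No outcome formula includes untested clients who buy no antimalarial, so the defined outcomes cannot show whether ACT purchase without a positive test fell per client

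*Combined protocol and SAP*

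**What the plan says.** Sections 2 and 3 state the scheme's ultimate goal as to "limit both inappropriate use of ACTs by those without a test or with a negative test", together with lower subsidy cost. The study's own objective is wider: "improving the management of suspected malaria fevers that seek care in the retail sector".

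Section 6.1 gives these denominators:

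- Primary: all ACTs sold. Buyers referred with a documented positive result count as positive.
- Testing uptake (the major secondary outcome) and secondary outcome 3 (appropriate management): clients tested with an RDT plus untested clients who bought an antimalarial.
- Secondary outcome 2 (adherence): clients tested with an RDT.
- Secondary outcome 4: "people who were not tested in the shop, did not have documentation of test and purchased any AM".

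The last secondary outcome is worded in two ways. The summary and section 6.1 list "ACT use by untested clients". Section 3 lists "ACT use by test status (untested, negative, positive") and gives no formula. Section 3 also plans the proportion of individuals using ACTs by test status, aggregated by outlet, but only to check agreement between exit interviews and provider reports.

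The interview base is also described in two ways. Section 3 has "Trained data collectors will approach customers who have transacted at the outlet". Section 4.1 has "All clients attending a participating outlet on the day selected for exit interviews will be eligible to be screened". Section 4.2 does not make a purchase a condition of eligibility. Item 4.1 of the exit questionnaire records every type of medicine obtained, and none is one of its answers.

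**The concern.** A client with fever who is not tested and leaves with a painkiller, or with nothing, is eligible and is interviewed (subject to the question about the interview base). That client is then in no outcome. Yet a move from buying an ACT untested to buying no antimalarial is one way in which the scheme's goal would be met.

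The primary is a share, so it can rise for two reasons: fewer ACTs go to untested or test-negative clients, or more ACTs go to test-positive clients, who receive them free in Arms 3 and 4. The first is a fall in misuse. The second is better access for confirmed cases and need not reduce misuse at all. (Misuse here means an ACT obtained without a positive test.) If the secondary outcomes cannot separate the two, the trial could report better targeting and still be unable to say whether misuse per client fell. The rate could be computed afterwards, but it would then be post hoc.

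**Working it through.** The plan states no figure for this quantity, so there is none to reproduce. The counts in steps 2 to 4 are assumed for illustration, except the 12%, 88% and 35% in step 2.

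**1. Structure.** Every numerator and denominator in section 6.1 is built from tested clients and untested antimalarial buyers; the primary adds documented referrals. Multiply all these counts by a constant c and every ratio is unchanged. If the number interviewed is fixed, misuse per client is multiplied by c, and untested non-buyers absorb the difference.

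**2. From the plan's expected percentages.** Section 6.2 expects 12% of ACTs to go to positives in the control arm (88% to others) and 35% in Arm 4. Take 100 control-arm ACTs and equal client numbers in the two arms. In Arm 4, ACTs to others = ACTs to positives × 0.65/0.35.

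| Arm 4 ACTs to positives | Arm 4 ACTs to others | Change from 88 |
|---|---|---|
| 12 | 22.3 | −75% |
| 47.4 | 88 | 0% |
| 60 | 111.4 | +27% |

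A primary of 35% therefore fixes neither the size nor the sign of the change in misuse.

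**3. All five outcomes together.** Take 1,000 interviewees and no outside tests.

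- Version A: 128 tested. Of 32 positives, 28 buy an ACT. Of 96 negatives, 12 buy an ACT and 84 buy no antimalarial. There are 48 untested antimalarial buyers (40 ACT) and 1,000 − 128 − 48 = 824 untested non-buyers.
- Version B: every tested and buyer count is tripled, leaving 1,000 − 384 − 144 = 472 untested non-buyers.

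| Outcome | A | B |
|---|---|---|
| Primary | 28/80 = 35.0% | 84/240 = 35.0% |
| Testing uptake | 128/176 = 72.7% | 384/528 = 72.7% |
| Secondary 2 | 112/128 = 87.5% | 336/384 = 87.5% |
| Secondary 3 | 112/176 = 63.6% | 336/528 = 63.6% |
| Secondary 4 | 40/48 = 83.3% | 120/144 = 83.3% |
| Misuse per client | 52/1,000 = 5.2% | 156/1,000 = 15.6% |

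The factor of 3 was chosen. The largest factor possible is 1 divided by the share of interviewees who are tested or buy an antimalarial: 1/0.176 = 5.7 in version A, but only 1/0.60 = 1.67 if that share is 60%.

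**4. Secondary outcome 4 alone.** In version A, let untested clients halve all antimalarial buying. The defined ratio stays at 83% (40/48, then 20/24). Over all 872 untested clients, ACT use falls from 40/872 = 4.6% to 20/872 = 2.3%.

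**5. Precision of a per-client outcome.** There are 170 interviews at each of 10 outlets, or 1,700 per arm. ICC 0.009 is the plan's value for the primary, assumed to carry over; 0.05 is an assumed higher value. The 14% rate is also assumed. It comes from Table 2: the 91% power for 19% versus 35% (alpha 1.667%, ICC 0.009) is reproduced with 25 ACT buyers per outlet (normal, 0.907) or 31 (t with 18 df, 0.907). These are 15% to 18% of 170, and 0.88 × 15% to 18% is 13% to 16%.

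- Design effect: 1 + 169 × 0.009 = 2.521 (effective n 674); 1 + 169 × 0.05 = 9.45 (effective n 180).
- 95% half-width: 2.10 × √(2 × 0.14 × 0.86/674) = 4.0 points; with n = 180, 7.7 points.
- A halving (14% to 7%, 7.0 points) has half-widths of 3.5 and 6.7. A 25% fall (3.5 points) has 3.7 and 7.2.

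**The case against.** The strongest reply is that the existing base is deliberate. Antimalarial buyers are a reasonable proxy for suspected malaria, the primary's complement is the share of ACTs going to untested or negative clients, and that serves both targeting and subsidy cost. This stands, and it is why the primary should be kept. The primary also does respond when untested clients buy less: in step 4 it rises from 28/80 = 35% to 28/60 = 47%. What it cannot do is tell that rise apart from one produced by extra purchases by positives.

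It can also be said that the numbers of ACT buyers and interviews would reveal a large shift. They would help, but no arm comparison of them is planned.

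The proposed rate has its own weakness: it falls if free ACTs draw in extra clients, without any fall in misuse. That must be stated with the result.

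Three stronger readings are tempting, and the documents do not support them.

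- A reader might infer that clients with a documented negative result enter the numerator of secondary outcome 4 but not its denominator. Section 6.1 defines untested clients as having no result from another facility, which keeps them out. The numerator line merely fails to repeat the condition. The paragraph that closes section 6.1 separately removes "those individuals who were referred from a health facility with a documented positive test result".
- A reader might infer that misuse per client can always differ several-fold at identical outcomes. That depends on the unstated share of untested non-buyers.
- A reader might infer that the plan has no per-client measure at all. Section 3 plans one for agreement between data sources, and its wording of the last secondary outcome could be read as one. What is missing is a formula and a between-arm comparison.

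**Conclusion.** The concern holds in this form. Untested clients who buy no antimalarial are outside every outcome that has a formula, and secondary outcome 4 does not measure what its label says. The defined outcomes therefore cannot show whether ACT purchase without a positive test fell per client, which is the misuse part of the scheme's stated goal. This follows from the formulas and needs no assumed counts. The possible size of the discrepancy does: the ceiling on the multiplier is 5.7 when 17.6% of interviewees are tested or buy an antimalarial, and 1.67 when 60% do, and the plan gives no share.

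This is a gap in the secondary outcomes and their labels. It does not invalidate the primary or the sample size. It is worth closing because the remedy is cheap and bears directly on the goal.

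**What to change.** 1. Keep the primary as it is.
2. For secondary outcome 4, take as denominator all untested interviewees without an outside test result (section 6.1's own definition), and repeat that condition in the numerator line. If the present ratio is kept, relabel it *ACT share of antimalarial purchases among untested clients*.
3. Add one supportive between-arm outcome with the same GEE model: obtained an ACT without a positive test, over all eligible consenting interviewees. Define positive exactly as for the primary: positive at the outlet, or referred from a health facility with a documented positive result. Derive it from questionnaire items 2.5 to 2.10, 3.1, 3.3 and 4.1. State the rule for invalid RDTs, for clients whom item 2.5 skips past the outside-test questions, and for mapping item 2.8 (which asks about any provider, facility or lab) to referral from a health facility. Read the primary alongside this outcome.
4. Align the wording of the last secondary outcome in the summary, section 3 and section 6.1.
5. State whether clients who buy nothing are interviewed (section 3 versus section 4.1). If they are not, call the new rate one per transacting client.

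The cost is SAP wording and one extra model on items already collected. Three downsides should be stated: one more secondary result, possible dilution if free ACTs attract extra clients, and limited precision. At the assumed 14% rate, a halving is resolved with ICC 0.009 and only just with ICC 0.05; a 25% fall is resolved with neither.
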